Contact Network Transmission Modeling of Healthcare Associated Infections: Identifying Effective Symptom-Based Markers for COVID-19 Transmission Study Protocol

Date: 7/23/2020

Version: 1.0

Principal Investigator: [name] [name]

Grant Number: U01CK000594

Project/Grant Period: 8/1/2020 – 7/31/2025

Clinical Trials Number: NCT04665245

Protocol Version and Amendment Tracking

Study Title: Contact Network Transmission Modeling of Healthcare Associated Infections: Identifying Effective Symptom-Based Markers for COVID-19 Transmission

Version Number/Amendment	Approval Date
Original Protocol, Version 1.0	07/23/2020

Protocol Synopsis

Protocol Title	Contact Network Transmission Modeling of Healthcare Associated Infections: Identifying Effective Symptom-Based Markers for COVID-19 Transmission
Main Criteria for Inclusion	Tested positive for COVID-19
Study Objective	To further the understanding of COVID-19 symptom development throughout the infection period, as well as how those symptoms vary at different points of the day.

Table of Contents

Protocol Version and Amendment Tracking	2
Protocol Synopsis	3
Table of Contents	4
1. Introduction.....	5
1.1 Background.....	5
2. Objective and Aim.....	5
2.1 Objective	5
3. Subject Inclusion/Exclusion Criteria	5
3.1 Inclusion Criteria	5
3.3 Exclusion Criteria	6
4. Study Design	6
4.1 Overview.....	6
4.2 Recruitment/Screening Procedures	6
4.3 Visit Procedures	6
4.4 Statistical Analysis Plan	7

1. Introduction

1.1 Background

One important approach for decreasing COVID-19 transmission in healthcare settings is to prevent healthcare professionals from working while ill. Currently, facilities are asking screening questions and measuring temperatures to help identify symptomatic healthcare professionals and exclude them from providing patient care. Simulations can be used to inform the effectiveness of different screening approaches, but the results of these simulations depend upon the effectiveness of the intervention, e.g., the ability to identify healthcare professionals on their way to work, or to study the impact of healthcare professionals returning to work too early. Thus, simulations must necessarily depend upon realistic disease parameters: for example, it is suspected that a non-trivial proportion of patients with COVID-19 may be asymptomatic or have minimal symptoms, but the relative size of the asymptomatic subpopulation is unknown.

The plan for this study is to develop a method for granular measurement of twice-daily symptoms from healthcare professionals and other research subjects of similar ages. After being diagnosed, the goal is to determine what symptoms participants have and how long they have had them. This will be done using a previously developed bidirectional texting platform to query participants about symptoms at least twice a day for ten days post diagnosis. Participants will be asked about subjective symptoms, including fevers, chills, cough, shortness of breath, fatigue, gastrointestinal symptoms, etc. They will also take their temperature twice daily during the recovery period, which will help determine the effectiveness of screening based on symptoms and/or thermometer readings.

2. Objective and Aim

2.1 Objective

The goal of this trial is to further the understanding of COVID-19 symptom development throughout the infection period, as well as how those symptoms vary at different points of the day.

3. Subject Inclusion/Exclusion Criteria

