4.3 Visit Procedures

We will collect the following data from the patient's medical record: date of birth, date of COVID test, type of COVID test, and COVID test number.

Immediately after the participant completes the online REDCap consent form, they will be

directed to the baseline survey. The baseline survey asks for the participant's cell phone number so that we can send them the twice daily survey, the time in the morning they wish to receive text messages, the time in the evening they wish to receive text messages, their mailing address for the compensation check, sex assigned at birth, if they are pregnant (if female), race, ethnicity, if they have any of a list of health conditions that have been shown to be related to worse COVID outcomes, if they are a smoker, and if they have a thermometer that they are able to use for the study. If they do not have a thermometer, we will drop one off outside their home so that they have one to use for the study.

Once that is complete, they will be entered into our bi-directional text messaging platform and sent 1 message every morning and 1 message every evening. These messages will remind them to measure their temperature and will ask about any current COVID-19 symptoms that they are experiencing. They will be sent text message reminders for 10 days.

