4.4 Statistical Analysis Plan

We will calculate summary statistics for participants' demographic characteristics (e.g., mean age, counts of comorbidities, percentage of females). We will also determine the progression of temperatures and symptoms over time. For example, we will determine when fevers occur, how many days fevers last, what symptoms are present, and how long symptoms last.

This is a descriptive pilot study, so no power analysis was performed or required. 500 was chosen as the number to enroll because we need a large sample of participants to learn about the various symptoms of this condition. Also, due to the remote nature of the study and the fact that the population is already known to be ill, we expect a large number of dropouts during the course of the study.

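### Does section 4.4 need a named morning-versus-evening summary and a rule for counting fever days?

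*Combined protocol and SAP*

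**What the plan says.** The objective in section 2.1 has two parts: how symptoms develop over the infection, "as well as how those symptoms vary at different points of the day". The synopsis and section 4.1 repeat it. Section 1.1 sets out to "develop a method for granular measurement of twice-daily symptoms" and to "query participants about symptoms at least twice a day for ten days post diagnosis". Under section 4.3 each participant is "sent 1 message every morning and 1 message every evening", at times the participant chooses, for 10 days. The messages ask about current symptoms and prompt a temperature reading.

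Section 4.4 is the only analysis section. After demographic summaries it says: "We will also determine the progression of temperatures and symptoms over time". It then gives examples: "we will determine when fevers occur, how many days fevers last, what symptoms are present, and how long symptoms last". It adds: "This is a descriptive pilot study, so no power analysis was performed or required". It sets enrolment at 500 and warns that "we expect a large number of dropouts during the course of the study". It gives no temperature threshold for fever, no rule for combining two readings in a day, and no rule for a day with only one reading.

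**The concern.** Part of the only objective appears to have no result attached to it. Twice-daily collection is there to show variation within the day, yet section 4.4 mentions neither morning nor evening. Of its examples, only the timing of fevers could be stretched to cover time of day, and that concerns fever alone. The rest are durations or a list of symptoms.

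The durations also look under-defined. With two readings a day, a fever day could mean either reading, both readings, or a count of half-days. If this were a real defect, the time-of-day question could go unanswered and two analysts could report different durations from the same data. Section 1.1 makes the point more than cosmetic: it motivates the study by screening healthcare staff on their way to work, where what can be detected at a given hour matters.

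**Working it through.** The plan has no figure to reproduce. The 500 is a chosen number, with no error rate, power, effect size or dropout rate behind it. The check is therefore a comparison of sections, plus arithmetic to see how much the silence could matter.

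**1. Objective against analysis.**
- Time-of-day part of the objective: synopsis, 2.1, 4.1.
- Data for it: one morning and one evening report per day (4.3).
- Analysis: the course of temperatures and symptoms over time (4.4), with examples that are not a closed list.

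The general commitment in 4.4 covers temperature and all symptoms, not only fever. Shown at the resolution at which the data are collected, it gives a morning and an evening value on each day. The wording permits the summary but does not name it.

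**2. Data available.** Per participant, 10 × 2 = 20 reports. For 500 participants, 500 × 20 = 10,000 reports, or 500 × 10 = 5,000 morning-evening pairs. These are upper limits, before dropout and missed replies. They also assume ten days from enrolment (4.3). Section 1.1 counts ten days from diagnosis, which would give late enrollees fewer.

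**3. Effect of the day rule, constructed example.** Take four days with (morning, evening) fever coded (0,1), (1,1), (1,1), (0,1).
- Either reading counts: 4 days.
- Both readings needed: 2 days.
- Half-days: 6 / 2 = 3 days.
- First to last febrile reading: evening of day 1 to evening of day 4, which is 4 calendar days or 4 − 1 = 3 elapsed days.

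The last is an ordinary reading of how long a fever lasts, and it needs no either-or-both rule.

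**4. Effect of the day rule, expected values.** Assumed inputs, not in the documents: fever probability 0.1 in the morning and 0.2 in the evening, within-day correlation φ from 0 to 0.6.
- P(both) = 0.1 × 0.2 + φ × √(0.1 × 0.9 × 0.2 × 0.8) = 0.02 + 0.12φ. Over 10 days this is 0.20 (φ = 0) to 0.92 (φ = 0.6).
- P(either) = 0.3 − P(both). Over 10 days this is 2.80 (φ = 0) to 2.08 (φ = 0.6).

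The choice of rule is material to the number reported. Every one of these rules is computed from the same stored readings, so choosing one at analysis costs no data.

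**5. Would prescribing a paired analysis help?** Let r be the reply rate, equal morning and evening, and c the within-day reply correlation (both assumed).
- Share of days with exactly one reading: 2r(1 − r)(1 − c).
- Share with none: (1 − r)² + c·r(1 − r).
- r = 0.9, c = 0.8: one reading 0.036; none 0.01 + 0.072 = 0.082; 0.036 / 0.918 = 3.9% of days with any reading.
- r = 0.5, c = 0: one reading 0.50; none 0.25; 0.50 / 0.75 = 67%.

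Restricting the main summary to complete pairs could thus discard between 3.9% and 67% of the days that carry information. An analysis of all readings is at least as defensible, so there is no clear gain in fixing the paired form in the plan.

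**The case for a change.** The strongest case for a change is that permission is not commitment. An objective stated three times should have a named result, and a few sentences in 4.4 would supply it with no new data and no change in sample size. A descriptive study still has to say which descriptions answer its question and how its durations are counted. Section 4.4 itself expects heavy dropout. Missed single replies are a different matter, but they too are likely among ill participants answering texts, so one-reading days will need handling.

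Much of this stands as fact. No section names the summary, defines fever or gives a day rule, and step 4 shows that the rule moves the number. What does not stand is the step from silence to defect. Nothing in 4.4 contradicts the objective or steers the analyst away from it. The added text would also fall short of reproducible durations unless it settled the definition of fever and whether day 1 is diagnosis (1.1) or enrolment (4.3). Participant-chosen message times mean that morning and evening are not fixed clock windows in any case.

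**Conclusion.** The concern is accurate about what section 4.4 omits, but the omission is a gap that analysts can fill sensibly, so no change to the plan follows. The objective is explicit, the data are collected morning and evening, and the general commitment in 4.4 covers the missing summary. With one cohort, no comparator and no hypothesis test, choosing the day rule at analysis creates no false-positive risk. Several rules can be reported side by side.

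The rule does affect the result: 4, 3 or 2 days in the constructed example, and about 0.2 to 0.9 against 2.1 to 2.8 expected fever days out of 10 under the assumed probabilities. Those inputs, and the reply rates in step 5, are illustrations; the documents give no fever frequency, reply rate or dropout rate. They show that a report must state its convention. They do not show that any figure or conclusion in the plan is wrong. The judgement assumes that individual readings are kept with their morning or evening label, which the messaging schedule in 4.3 implies.

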3.1 Inclusion Criteria

- Age 18 – 100 years
- Able to speak and read English
- Have tested positive for COVID-19

3.3 Exclusion Criteria

- prisoner status
- unable to provide own written informed consent

4. Study Design

4.1 Overview

In this study, COVID-19 positive patients will be added to a bidirectional texting program to receive daily surveys about their symptoms with the infection. This data will further the understanding of COVID-19 symptom development throughout the infection period, as well as how those symptoms vary at different points of the day. This study will be a single cohort, observational study of COVID-19 patients.

4.2 Recruitment/Screening Procedures

The research team will identify potentially eligible subjects by screening the COVID-19 Positive Results for Research report that is created in Epic. When a potentially eligible subject is identified, they will be contacted using the email address available in Epic. The potentially eligible subject will be sent an email with screening questions to determine their full eligibility (<https://redcap.link/pgpqjs7n>). If they are fully eligible, they will be directed to a REDCap informed consent document for them to electronically sign and return to the team.

If participants do not respond to the initial email, they will be sent 1 additional email to see if they are interested in the study. If they still do not respond, they will not be contacted further.

We will minimize coercion by telling them that their participation in the study is completely voluntary and will not have any impact on their treatment. Since the consent process takes place remotely, they will easily be able to read the study information and not complete the form, if they wish.

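### Care setting, hospital admission and death are not recorded, so replies that stop at admission cannot be told apart from ordinary non-response

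*Combined protocol and SAP*

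**What the plan says.** Eligibility (protocol 3.1 and 3.3) rests on age 18 to 100, English, and "Have tested positive for COVID-19". The only exclusions are prisoner status and being "unable to provide own written informed consent". Neither list mentions hospitalisation.

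Recruitment (4.2) works by "screening the COVID-19 Positive Results for Research report that is created in Epic"; no outpatient limit on that report is described. Candidates are then "sent an email with screening questions to determine their full eligibility". The content of those questions is not given.

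Data collection (4.3) takes four items from the medical record: "date of birth, date of COVID test, type of COVID test, and COVID test number". The baseline survey covers contact details, preferred text times, sex, pregnancy, race, ethnicity, smoking, thermometer access, and "if they have any of a list of health conditions that have been shown to be related to worse COVID outcomes". The morning and evening texts, sent for 10 days, prompt a temperature reading and ask about current symptoms. For a participant without a thermometer, "we will drop one off outside their home so that they have one to use for the study".

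Analysis (4.4) promises the timing and length of fevers, and which symptoms occur and for how long. It sets enrolment at 500 without a power calculation and expects heavy dropout, partly because participants are already ill. It gives no dropout rate, no plan to record reasons, and no rule for a duration when replies stop.

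**The concern.** Two of the outputs named in 4.4 are durations, and the only source for them is the participant's replies. A duration observed this way can run no further than the last reply. If replies stop because the participant was admitted or died, the missing part belongs to a severe course, so the loss depends on the quantity being measured. The plan foresees loss related to illness but collects nothing that would show which losses are of this kind.

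There is a second, smaller gap. Someone in hospital who goes on texting contributes temperatures and symptoms observed in hospital, and nothing in the data marks them. Section 1.1 wants the findings to inform efforts to "prevent healthcare professionals from working while ill", so a reader will want to know how much of the described course comes from people who were in hospital. As planned, the report could not say.

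**Working it through.** **The plan's own figure.** The 500 in 4.4 has no inputs behind it (no precision target or dropout rate), so there is nothing to reproduce. The point turns on what is collected.

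**Step 1: trace four participants through 4.3.**

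| Participant | Replies held | Marker in the planned data |
|---|---|---|
| Admitted on day 4, stops replying | days 1–3 | none |
| At home, stops replying on day 4 for another reason | days 1–3 | none |
| Admitted on day 4, keeps replying | days 1–10 | none |
| In hospital at consent, keeps replying | days 1–10 | none |

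The first two have the same pattern of replies, up to 3 × 2 = 6 out of 10 × 2 = 20. The last two look like someone at home. The content of the last replies may hint at worsening, but it does not record why they stopped.

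**Step 2: effect on mean duration (all rates assumed).** Suppose a share *a* of participants last reply on day 3 and truly have symptoms through day 10. If duration ends at the last reply, each loses 10 − 3 = 7 days, and the mean over the cohort falls by 7*a*:

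- *a* = 2% (10 of 500): 7 × 0.02 = 0.14 days
- *a* = 5% (25 of 500): 7 × 0.05 = 0.35 days
- *a* = 10% (50 of 500): 7 × 0.10 = 0.70 days

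This counts only the 10 text days.

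**Step 3: could such losses be spotted among other dropouts?** If a share *d* of the non-admitted also drop out, admissions make up *a* / (*a* + (1 − *a*)*d*) of all dropouts. For *a* = 2% this is 9.3% at *d* = 20% and 4.9% at *d* = 40%. For *a* = 10% it is 35.7% and 21.7%. The planned data cannot say where in this range the study lies.

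**Step 4: effect on how often fever is seen, at its most extreme.** Assume true fever prevalence of 30%, 80% among those admitted, and no data at all from the admitted. Observed prevalence is (0.30 − 0.80*a*)/(1 − *a*):

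- *a* = 2%: 0.284/0.98 = 29.0% (−1.0 points)
- *a* = 5%: 0.260/0.95 = 27.4% (−2.6 points)
- *a* = 10%: 0.220/0.90 = 24.4% (−5.6 points)

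The 95% half-width at 30% with n = 500 is 1.96 × √(0.30 × 0.70/500) = 4.0 points, so only the 10% case exceeds it. Replies sent before admission are in fact kept, so for these inputs the true effect on prevalence is smaller.

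**Step 5: effect of mixing settings at enrolment (all rates assumed).** With shortness of breath at 25% at home and 80% in hospital, an inpatient share of 2% gives 0.98 × 25% + 0.02 × 80% = 26.1%, and 5% gives 27.75%. Both shifts (1.1 and 2.75 points) lie inside the 95% half-width of 1.96 × √(0.25 × 0.75/500) = 3.8 points. For fever even the direction is open. From 30% at home, a 5% inpatient share gives 31.5% if inpatients have 60% fever, and 29.3% if treatment lowers theirs to 15%.

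**The case against.** The strongest reply is that this is a descriptive pilot whose stated objective (2.1) and overview (4.1) concern COVID-19 positive patients in general. On that reading an inpatient belongs in the cohort and is not a source of bias. This stands. A reader might infer from the motive in 1.1 and the home thermometer delivery in 4.3 that the study targets people in the community, and that outpatients should therefore be the main analysis group. No section says so. Making outpatients the main group would redefine the population, and the point does not need it.

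Second, inpatients are eligible only by omission, and the unseen screening questions or the Epic report may filter them. Contact by at most two emails, electronic consent, texting and home delivery also make a large inpatient share unlikely. This stands as a limit on size. It does not close the gap, because the listed criteria give the screening questions no ground to exclude on setting, and without the item a low share cannot be shown.

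Third, a reader might infer that severe courses vanish from the data altogether. They do not: replies sent before admission are kept and count towards which symptoms occur. What is lost is the later course, the true duration, and the reason that replies stopped.

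Being a pilot explains the absence of a power analysis. It does not excuse leaving unrecorded who is described, since description is the study's only product.

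**Conclusion.** The gap is real and narrow. Care setting is unrestricted in 3.1, 3.3 and 4.2, and setting, admission and death are not among the items in 4.3. Durations for participants who stop replying on admission are cut short by severity and cannot be separated from other non-response; those who keep replying from hospital are taken for people at home.

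The size cannot be derived from the documents, and every rate used above is assumed. On those assumptions the duration effect is 0.14 to 0.70 days in the mean for 2% to 10% affected. Mixing at enrolment probably matters less than loss through later admission. The documents do not support a claim that the cohort is substantially contaminated by inpatients. This is a cheap improvement and does not undermine the study.

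**What to change.** In 4.3, add to the chart data: care setting on the consent date, and any hospital admission or death with its date within the 10 text days. Take these in one chart check after day 10.

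In 4.4:

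- Describe the cohort by care setting at consent.
- Show symptom and temperature results with and without inpatients.
- Report how many participants stopped replying at or after admission or death.
- Treat the fever and symptom durations of those participants as incomplete, not as ended at the last reply. An estimate that censors them at the last reply assumes they resemble those who stay, which is doubtful after admission, so show the count beside it.

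The cost is a second look at a chart already being accessed, for up to 500 people, and a line in the consent form. The existing chart items are fixed at the test date, so this check is extra work. Admissions outside the health system may be missed and would still look like ordinary dropout; the report should say so. Eligibility and sample size stay as they are.

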4.3 Visit Procedures

We will collect the following data from the patient's medical record: date of birth, date of COVID test, type of COVID test, and COVID test number.

Immediately after the participant completes the online REDCap consent form, they will be

directed to the baseline survey. The baseline survey asks for the participant's cell phone number so that we can send them the twice daily survey, the time in the morning they wish to receive text messages, the time in the evening they wish to receive text messages, their mailing address for the compensation check, sex assigned at birth, if they are pregnant (if female), race, ethnicity, if they have any of a list of health conditions that have been shown to be related to worse COVID outcomes, if they are a smoker, and if they have a thermometer that they are able to use for the study. If they do not have a thermometer, we will drop one off outside their home so that they have one to use for the study.

Once that is complete, they will be entered into our bi-directional text messaging platform and sent 1 message every morning and 1 message every evening. These messages will remind them to measure their temperature and will ask about any current COVID-19 symptoms that they are experiencing. They will be sent text message reminders for 10 days.

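### No listed item records why participants were tested or their symptoms before enrolment, so pooled symptom and fever frequencies may not transfer to screening

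*Combined protocol and SAP*

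**What the plan says.** Section 4.2 finds candidates by "screening the COVID-19 Positive Results for Research report that is created in Epic". The only disease criterion in section 3.1 is "Have tested positive for COVID-19"; nothing there refers to symptoms or to the reason for the test.

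Section 4.3 lists three sources of data:

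- **Medical record:** "date of birth, date of COVID test, type of COVID test, and COVID test number".
- **Baseline survey:** contact and texting details, sex, pregnancy, race, ethnicity and health conditions, ending with "if they are a smoker, and if they have a thermometer that they are able to use for the study".
- **Texts, morning and evening for 10 days:** a reminder to take the temperature, and a message that "will ask about any current COVID-19 symptoms that they are experiencing".

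Section 4.4 then reports, for the cohort as a whole, when fevers occur and how long they last, and "what symptoms are present, and how long symptoms last". It plans no split by route to testing and states no limitation on this point.

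Section 1.1 gives the purpose. Simulations of workplace screening need realistic disease parameters, and the example given is that "the relative size of the asymptomatic subpopulation is unknown". The same section expects the readings to show how well screening by symptoms or thermometer works.

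**The concern.** A list of positive tests contains only people whom someone decided to test. If symptoms prompted part of that testing, symptomatic infections are over-represented on the list. The share with fever, or with any given symptom, is then higher than among all infected people, and the share with no symptoms is lower. Read as the chance that a screening question or thermometer would flag an infected worker, such a figure is too favourable.

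The mix of reasons for testing might be harmless or might matter a great deal. Under the listed data items nobody could find out afterwards. No listed item records the reason for the test, and the type of test is not described as standing in for it.

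A second gap compounds this. The texts cover current symptoms after enrolment only. A person whose symptoms ended before the first text would appear to have had none.

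**Working it through.** **The plan's own figure.** The only number in section 4.4 is the enrolment target of 500. It comes with no precision target, rate or error level, so there is no calculation to reproduce.

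**Inputs.** From the documents: N = 500, entry by positive test, and no recorded reason for testing. Assumed, because the documents give no values:

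- p, the true share of infections without symptoms: 30%, with 20% and 40% as alternatives.
- r, the testing rate of infected people without symptoms relative to those with symptoms: 0.1 to 1.
- F, the share of symptomatic people with fever: 60%. People without symptoms have none.
- Test sensitivity and response to the email do not differ by symptoms, so that the effect of testing is seen alone.

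**Formulas.** Per infected person, the tested-positive group is made up of pr without symptoms and (1 − p) with symptoms. Hence:

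- observed no-symptom share = pr / (pr + 1 − p)
- observed fever share = F(1 − p) / (pr + 1 − p)
- true fever share = F(1 − p) = 0.6 × 0.7 = 42%

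**Results at p = 30%.**

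| r | No-symptom share (true 30%) | Fever share (true 42%) |
|---|---|---|
| 0.1 | 0.03/0.73 = 4% | 0.42/0.73 = 58% |
| 0.3 | 0.09/0.79 = 11% | 0.42/0.79 = 53% |
| 0.5 | 0.15/0.85 = 18% | 0.42/0.85 = 49% |
| 1 | 0.30/1.00 = 30% | 0.42/1.00 = 42% |

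**Other true shares.** At r = 0.1, 0.5 and 1, the observed no-symptom share is 2.4%, 11.1% and 20% when p = 20%, and 6.3%, 25% and 40% when p = 40%.

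**Against sampling error.** With all 500 contributing, the 95% half-width at 30% is 1.96 × √(0.3 × 0.7/500) = 4.0 points. The shift at r = 0.5 is 30 − 17.6 = 12.4 points, about three times that. The shift equals 4 points where 0.3r/(0.3r + 0.7) = 0.26, that is r = 0.182/0.222 = 0.82. Enrolling more people narrows the interval but leaves the shift unchanged.

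**Precision if the reason is recorded.** In the group not tested for symptoms, at an assumed 30% share, the half-width is 1.96 × √(0.21/n): 5.7 points for n = 250, 8.0 for n = 125 and 12.7 for n = 50, before dropout.

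**The case against.** The strongest reply is that the study does not set out to estimate an asymptomatic share. The objective in section 2.1 is the course of symptoms and their variation over the day. Section 4.4 lists timing, duration and type of symptoms, and calls the work a descriptive pilot. Section 1.1 mentions the asymptomatic group only as an example of a parameter that simulations need. This stands. Timing, duration and time-of-day pattern among symptomatic participants are not what the formulas above distort. What remains exposed is the frequency of symptoms and fever, which section 4.4 does plan to describe, and the screening use in section 1.1.

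It can also be said that every magnitude is assumed, and that if routine or exposure testing dominated locally the effect could be small. That stands too: at r = 1 there is no shift. It does not remove the point, because the listed data would not show which case applies.

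Finally, the email's "screening questions to determine their full eligibility" and the wording of the texts are not reproduced, so an unlisted item cannot be ruled out. No listed eligibility criterion would call for asking why the test was done.

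**Conclusion.** The point holds as a recommended improvement. As listed, the data describe people who were tested, positive and enrolled, and give no means of examining how testing shaped the symptom and fever frequencies. The direction is conditional. If people without symptoms are tested less often (r < 1), testing alone pushes symptom and fever frequencies up and the no-symptom share down. On the assumptions shown, the no-symptom share falls from 30% to between 4% and 18% for r from 0.1 to 0.5, and fever rises from 42% to between 58% and 49%. Symptoms that ended before the first text would work the other way, so the net error in a no-symptom figure cannot be signed from the listed data.

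A reader might infer three stronger things that the documents do not support:

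- **That the cohort is selected on symptoms.** Entry requires a positive test and nothing more. How far testing depended on symptoms is not stated.
- **That a planned endpoint is wrong.** No asymptomatic share is listed in section 4.4.
- **That people tested for other reasons are an unselected group.** They must still answer an email and consent, which may depend on how ill they feel. Without a question on earlier symptoms, their no-symptom figure would not be usable either.

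**What to change.** Add two items to the REDCap baseline survey in section 4.3:

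1. Why were you tested? (symptoms; contact with a case; routine, pre-procedure or work screening; other)
2. Have you had any symptoms before or since the test, and when did they start?

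In section 4.4, report symptom, fever and no-symptom frequencies separately for symptom-triggered and other tests. Base any no-symptom or screening-yield figure on the other tests, counting symptoms reported at baseline as well as by text. State that the results apply to people with a positive test who responded to the invitation.

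The cost is two questions in a survey that every participant is already sent to, and one split in the tables. Recruitment and follow-up do not change. The drawback is precision: the half-width grows from 4.0 points on all 500 to between 5.7 and 12.7 points for subgroups of 250 down to 50. Selection by response to the email also remains and should be named as a limitation. The second item relies on recall.
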